2.2 Clinical Hypotheses

[figure not shown]
- BOTOX is more effective than topiramate as measured by the difference between treatment groups in a 50% responder rate (defined as the proportion of patients with a $\geq 50\%$ reduction from baseline in the number of headache days over a 28-day period).
- BOTOX has a superior tolerability profile than topiramate as measured by the difference between treatment groups in the rates of adverse events and discontinuations due to adverse events.
- BOTOX has an acceptable safety profile.

3. Study Design

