3.1 Structure

This is a prospective, multicenter, randomized, open-label, parallel-group, post-authorization study to evaluate the efficacy, safety, and tolerability of BOTOX versus topiramate in adult patients with CM. The study consists of a pretreatment period lasting 4 weeks, a treatment period with BOTOX or topiramate treatment lasting up to 36 weeks, and a posttreatment follow-up period lasting 12 weeks (for patients receiving BOTOX) (Figure 1). All randomized patients are to remain in the study until week 36. However, patients who discontinue topiramate treatment on or before week 36 will crossover to treatment with BOTOX and remain in the study until week 48. Therefore, a patient could remain in the study for a maximum of 54 weeks. Patients are required to maintain a daily electronic headache diary (e-diary) the during the entire study period (ie, screening visit to exit visit).

Figure 1 Study Design

The pretreatment period consists of a screening visit that occurs within 6 weeks prior to day 1 and a prospective 28-day run-in period. The prospective run-in period should begin as soon as the patient completes the screening procedures. Patients who complete the run-in period

and meet the prespecified entry criteria will be randomized on day 1 in a 1:1 ratio to receive BOTOX or topiramate. For data analysis purposes, the number of headache days during the first 28 continuous days of the run-in period will serve as the “baseline” for calculating change from baseline for 28-day periods subsequent to each office visit.

The treatment period consists of patients receiving either IM injections of BOTOX 155 U approximately every 12 weeks or up to 100 mg/day of oral topiramate administered daily up to week 36. Patients randomized to BOTOX will receive 3 treatment sessions of BOTOX 155 U (at day 1, week 12 \pm 7 days, and week 24 \pm 7 days) according to the fixed-site, fixed-dose injection paradigm. The final/exit visit for these patients will be at week 36 (or approximately 12 weeks after the last injection) (see Section 5.4.1 for details).

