not exceed 100 mg/day ([Topamax[®] US package insert, 2012](#)). At the next scheduled office visit (ie, week 12), the investigator, at his/her discretion, may adjust the topiramate dose (upward or downward) to be within the range of 50 to 100 mg/day; the patient should remain on this dose for the remainder of topiramate treatment in the study. For all patients completing topiramate treatment or those who discontinue from treatment, a dose taper period of up to 2 weeks is recommended. Refer to Section 5.4.2 for further details.

Patients who complete topiramate treatment at week 36 will be exited from the study at week 36. Patients who discontinue topiramate treatment at any time up to or including week 36 will crossover to receive treatment with BOTOX 155 U for the remainder of the study. The first BOTOX treatment will be administered at the next scheduled office visit, and the patient will return every 12 weeks up to and including the week 36 visit to receive BOTOX treatments, with a final exit visit at week 48. BOTOX treatment can be initiated during the topiramate dose tapering period.

All patients receiving BOTOX in the study will be followed for 12 weeks after the last injection.

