5.4.2.2 Dose Maintenance

Starting at week 4 (ie, the maintenance phase), the patient should remain on a stable topiramate dose of at least 50 mg/day. As per the recommended topiramate dose for migraine prophylaxis, the topiramate dose must not exceed 100 mg/day ([Topamax[®] US package insert, 2012](#)). At the next scheduled office visit (ie, week 12), the investigator, at

his/her discretion, may adjust the topiramate dose (upward or downward) to be within the range of 50 to 100 mg/day; the patient should remain on this dose for the remainder of topiramate treatment in the study.

For all patients who complete topiramate treatment or who discontinue from treatment, a dose taper period of up to 2 weeks is recommended. The investigator will determine the duration of the taper, which is based on the maximum dose received during the maintenance phase.

Patients who discontinue topiramate at any time up to or including week 36 will crossover to receive treatment with BOTOX 155 U for the remainder of the study. The first BOTOX treatment will be administered at the next scheduled office visit, and the patient will return every 12 weeks up to and including the week 36 visit to receive BOTOX treatments, with a final exit visit at week 48. BOTOX treatment can be initiated during the topiramate dose tapering period.

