5.7 Treatment Administration

Following a 28-day run-in period, patients meeting the inclusion/exclusion criteria will receive their first treatment at visit 2 (day 1). On day 1, patients will be randomized in a 1:1 ratio to receive IM BOTOX 155 U administered approximately every 12 weeks or up to 100 mg/day oral topiramate administered daily, up to week 36. Patients who discontinue topiramate treatment on or before the week 36 visit will receive treatment with BOTOX for the remainder of the study.

Patients randomized to receive BOTOX treatment will receive 3 treatment sessions of BOTOX according to the US labeled injection paradigm (see Section 5.4.1) over the course of the study, ie, at day 1, week 12 ± 7 days, and week 24 ± 7 days.

Patients randomized to receive topiramate treatment will receive up to 36 weeks of topiramate administered orally at doses starting at 25 mg/day given once daily and tapered up to 100 mg/day given twice daily. Patients will continue to receive daily doses of topiramate until week 36 or early discontinuation (with dose tapering to commence at the time of discontinuation).

Patients who discontinue topiramate treatment prior to week 36 will be asked to return to the office at the next scheduled visit to receive treatment with BOTOX. These patients will receive IM injections of BOTOX 155 U approximately every 12 weeks up to and including the week 36 visit, for a maximum of 3 BOTOX treatment sessions during the course of the study. BOTOX treatment can be initiated during the topiramate dose tapering period.

All patients receiving BOTOX in the study will be followed for approximately 12 weeks after the last injection.

6. Response Measures and Summary of Data Collection Methods

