8.8 Early Discontinuation of Patients

Patients may voluntarily withdraw consent from the study at any time. If the patient withdraws consent due to any reasons other than treatment discontinuation (eg, patient moved, patient does not complete visits), all of the final measurements should be performed at the exit visit and recorded on the appropriate eCRF. The eCRF for patient treatment discontinuation should be completed to document patient withdrawal of consent.

If a patient discontinues topiramate treatment, the eCRF for patient treatment discontinuation should be completed to document the reason for discontinuation. The patient should not be

exited from the study, but should be administered BOTOX at the next scheduled office visit (ie, week 12, 24, or 36).

If a patient discontinues BOTOX treatment, the eCRF for patient treatment discontinuation should be completed to document the reason for discontinuation. The patient should then be exited from the study and all of the final measurements should be performed at the exit visit and recorded on the appropriate eCRFs.

If a patient is determined as a loss to follow-up, the eCRF for patient treatment discontinuation should be completed to document the reason for discontinuation.

If a patient must exit the study due to pregnancy or the C-SSRS (ie, the patient answers “yes” to questions 4 or 5 in the suicidal ideation section or “yes” to any question in the suicidal behavior section), the eCRF for patient treatment discontinuation should be completed to document the reason for discontinuation. The patient should then be exited from the study and all of the final measurements should be performed at the exit visit and recorded on the appropriate eCRF.

Notification of early patient discontinuation from the study and the reason for discontinuation will be made to Allergan or Allergan designee and will be clearly documented on the appropriate eCRF.

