## 3. Investigational Plan

### 3.1. Overall Study Design and Plan

[figure not shown]
This is a prospective, multicenter, randomized, open-label, parallel-group, post-authorization study to evaluate the efficacy, safety, and tolerability of BOTOX versus topiramate in adult patients with CM. The study consists of a pretreatment period lasting 4 weeks, a treatment period with BOTOX or topiramate treatment lasting up to 36 weeks, and a post-treatment follow-up period lasting 12 weeks (for patients receiving BOTOX) (Figure 1). All randomized patients are to remain in the study until Week 36; however, patients who discontinue topiramate treatment on or before Week 36 will switch over to treatment with BOTOX and remain in the study until Week 48. Therefore, a patient could remain in the study for a maximum of 54 weeks. Patients are required to maintain a daily electronic headache diary (eDiary) during the entire study period (i.e., screening visit to exit visit).

The pretreatment period consists of a screening visit that occurs within 6 weeks prior to Day 1 and a prospective 28-day run-in period. The prospective run-in period should begin as soon as the patient completes the screening procedures. Patients who complete the run-in period and meet the prespecified entry criteria will be randomized on Day 1 in a 1:1 ratio to receive BOTOX or topiramate. Approximately 400 patients (200 patients per arm) will be enrolled at approximately 40 US sites. For data analysis purposes, the number of headache days during the first 28 calendar days of the screening period starting on the day of eDiary Touch device setup will serve as the “baseline” for calculating change from baseline for 28-day periods subsequent to each office visit.

The treatment period consists of patients receiving intramuscular (IM) injections of either BOTOX 155 U approximately every 12 weeks or up to 100 mg/day of oral topiramate administered daily up to Week 36. Patients randomized to BOTOX will receive 3 treatment sessions of BOTOX155 U (Day 1, Week 12 ± 7 days, and Week 24 ± 7 days) according to the fixed-site, fixed-dose injection paradigm. The final/exit visit for these patients will be at Week 36 (or approximately 12 weeks after the last injection).

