**Table 3: BOTOX Compliance Formula**

Time to Next BOTOX Injection	BOTOX Compliance Formula
+/- 7 days from the visit schedule	$\text{Min} \left( \frac{\text{Units Injected}}{155 \text{ U}}, \frac{\text{Sites Injected}}{31 \text{ Sites}} \right) * 100\%$
+/- 8 to 10 days from the visit schedule	$\text{Min} \left( \frac{\text{Units Injected}}{155 \text{ U}}, \frac{\text{Sites Injected}}{31 \text{ Sites}}, 0.90 \right) * 100\%$
+/- 11 to 14 days from the visit schedule	$\text{Min} \left( \frac{\text{Units Injected}}{155 \text{ U}}, \frac{\text{Sites Injected}}{31 \text{ Sites}}, 0.80 \right) * 100\%$

+/- 15 or more days from the visit schedule	0%
---	----

For both the BOTOX and topiramate treatment arms, the number and percentage of patients in each compliance rate category (<80%, 80% – 100%, 100% – 120% and >120% as well as <80% and ≥80%) will be reported. If the treatment compliance is less than 80% or greater than 120% and treatment discontinuation is reported at the subsequent office visit, then date of last treatment taken/received from either the eCRF or the eDiary will be the reported as date of discontinuation. Percentages will be calculated from the number of patients who have received treatment in the study period.

If a patient discontinues topiramate treatment, the eCRF for treatment discontinuation must be completed to document the reason for discontinuation. The patient should not be exited from the study, because BOTOX must be administered at the next scheduled office visit (ie, Week 12, 24, or 36).

If a patient discontinues BOTOX treatment, the eCRF for treatment discontinuation must be completed to document the reason for discontinuation and the patient will be exited from the study.

Treatment compliance will be summarized for the Safety Set. Patients will be counted in the treatment arm in which treatment was received. The study drug compliance rate will be summarized using descriptive statistics. Counts and percentage of patients in each compliance rate category will be provided. Denominators for percentages will be the total number of patients who received treatment in each treatment arm and overall.

BOTOX treatment administration by visit, topiramate drug accountability, and topiramate drug accountability per eDiary will be presented in data listings.

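### SAP 9 and SAP 9.1 end the treatment-emergent AE window at different visits; the 9.1 rule drops Weeks 36 to 48 for patients who switch to BOTOX

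*Protocol*

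**What the plan says.** **End of the TEAE window.** SAP 9 counts AEs that start or worsen between the first dose and the final visit. SAP 9.1 has the same start, but its two dated bullets require onset or worsening before the Week 36 office visit. Its third bullet admits an AE with a wholly missing onset date if it ended on or after the first dose, and sets no upper limit.

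**Who is still in the study after Week 36.** Under Protocol 5.4.2.2, patients who stop topiramate return "every 12 weeks up to and including the week 36 visit to receive BOTOX treatments, with a final exit visit at week 48". SAP 3.1 gives the same Week 48 exit. Patients who complete their randomised treatment leave at Week 36.

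**What the AE tables should hold.** SAP 9 makes the topiramate + BOTOX patients a subset of the BOTOX column, so they are in its N. It says that the subset's summary covers every TEAE after the switch. SAP 9.1.1 adds a TEAE summary for each injection cycle. No safety testing is planned. Protocol 2.2 measures the tolerability hypothesis by the treatment difference "in the rates of adverse events and discontinuations due to adverse events".

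**Retention.** Protocol 3.1 states: "All randomized patients are to remain in the study until week 36". SAP 3.1 repeats this with a single exception: "All randomized patients are to remain in the study until Week 36; however, patients who discontinue topiramate treatment on or before Week 36" move to BOTOX and stay to Week 48. Protocol 8.8 says a patient who stops BOTOX should "be exited from the study and all of the final measurements should be performed at the exit visit and recorded on the appropriate eCRFs". SAP 7.2 agrees: the discontinuation eCRF is completed "to document the reason for discontinuation and the patient will be exited from the study". Protocol 3.3 adds "All patients receiving BOTOX in the study will be followed for 12 weeks after the last injection", and Protocol 5.7 says "All patients receiving BOTOX in the study will be followed for approximately 12 weeks after the last injection".

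**The concern.** The two TEAE definitions give different tables from the same data. A programmer who follows SAP 9 includes a switcher's events to Week 48. One who follows SAP 9.1 stops at Week 36, the day on which that patient may receive a BOTOX injection. The second reading also defeats two outputs that the SAP itself plans: the full post-switch summary and the table by injection cycle. What is at stake is the BOTOX column of the AE tables, which is the evidence for the AE-rate half of the tolerability hypothesis.

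Separately, the design overviews say that everyone stays to Week 36, while the discontinuation rules exit patients who stop BOTOX. Protocol 8.8 does not itself say when that exit visit takes place.

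**Working it through.** The plan gives no figure for this point. Its 200 per group (28% v 44%, 90% power, two-sided 0.05, continuity-corrected) reproduces as 200 and is used below only as the BOTOX N.

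**Inputs.** Switchers' final visit, Week 48 (SAP 3.1). SAP 9.1 cut, Week 36. First BOTOX injection for switchers at Week 12, 24 or 36 (Protocol 8.8). BOTOX exposure runs to 84 days after the last injection (SAP 7.1).

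**1. Where the definitions differ.**

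| Group | SAP 9 end | SAP 9.1 end | Gap |
|---|---|---|---|
| Completers, either arm | Week 36 visit | before Week 36 visit | at most the visit day |
| Switchers | Week 48 visit | before Week 36 visit | 48 − 36 = 12 weeks |

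**2. Share of a switcher's BOTOX follow-up lost.** For first injection at Week w, the share is 12 / (48 − w).

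| w | Planned follow-up | Lost | Share | Cycle lost |
|---|---|---|---|---|
| 12 | 36 weeks | 12 | 33% | third of three |
| 24 | 24 weeks | 12 | 50% | second of two |
| 36 | 12 weeks | 12 | 100% | the only one |

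A patient first injected at Week 36 is in the BOTOX N with no event time.

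**3. Direction.** N is the number who received BOTOX and does not depend on the window. A shorter window can only remove patients from the numerator, so the BOTOX percentage falls or stays the same. The topiramate column can lose events too, because SAP 9 assigns a switcher's post-injection TEAEs to the treatment the physician considers related, or to both.

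**4. Size under assumed numbers.** The documents do not give the number of switchers. Assume s = 20 to 100, all first injected at the same visit, and 200 BOTOX patients followed for 36 weeks. The share of pooled BOTOX person-time lost is 12s / (200 × 36 + s(48 − w)):

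- s = 20, w = 12: 240 / 7,920 = 3.0%; w = 36: 240 / 7,440 = 3.2%
- s = 100, w = 12: 1,200 / 10,800 = 11.1%; w = 36: 1,200 / 8,400 = 14.3%

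As an extreme case, let every switcher start at Week 36, with an assumed true rate of 50% and all events attributed to BOTOX. The column would then show 100/220 = 45.5% (s = 20) or 100/300 = 33.3% (s = 100) instead of 50%. This is an outer limit for the assumed s and rate, not an estimate.

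**5. BOTOX stoppers.** The exposure window is 84/7 = 12 weeks. A patient who stops at the next scheduled visit has completed it, so 12 − 12 = 0 weeks are lost. The time to Week 36 that is not followed is 36 − 12 = 24 weeks (exit at Week 12) or 36 − 24 = 12 weeks (exit at Week 24), all outside the window. An earlier exit would breach the follow-up in Protocol 3.3 and 5.7.

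**The case against.** The best defence of SAP 9.1 is that its Week 36 end was meant for the first lock. SAP 1 does plan a lock after Week 36, but the same section says the plan covers both the primary and the final analysis, and SAP 9.1 does not tie its cut to either. It is also fair that SAP 9 already shows the intent, that AEs are recorded throughout and listed by patient, and that nothing is tested. All of that stands and keeps the point minor. Protocol 7.3.3, 8.4 and Table 1 cannot be read in the public copy, so a protocol-level definition or an exit date may exist there. The conflict inside the SAP would remain.

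A reader might infer more than the documents support:

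- **That exiting BOTOX stoppers distorts efficacy or loses BOTOX exposure.** SAP 3.4 and 8.1.1 make early stoppers in both arms nonresponders with baseline values, so primary and secondary results do not change. Step 5 shows no exposure lost at a scheduled stop. SAEs are reportable for at least 12 weeks after the last dose (Protocol 9.3). Protocol 8.8 and SAP 7.2 agree as the specific rule, and the Week 36 sentence also omits the pregnancy and C-SSRS exits, so it was never exhaustive. Following BOTOX stoppers to Week 36 is a design preference, not a required amendment.
- **That BOTOX stoppers drop out of the observed-data sensitivity analysis.** SAP 8.1.2 item 3 lifts only the imputation for periods with fewer than 20 diary days. Nothing in it suspends the SAP 3.4 nonresponder rule.
- **That the AE comparison must be re-based on randomised treatment.** SAP 9 sets out an as-treated attribution scheme, in line with Protocol 7.1. One may prefer another, but the scheme is not an error.

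**Conclusion.** The TEAE definitions conflict in the current SAP. If SAP 9.1 is followed, every switcher loses 12 weeks, which is 33%, 50% or 100% of planned BOTOX follow-up depending on the switch visit, and the BOTOX TEAE percentage can only fall or stay the same. These shares follow from the visit schedule and assume that the switcher attends to Week 48. They concern new or worsening AEs with known dates. The effect on the reported percentages cannot be computed, because neither the number of switchers nor the AE rates are given; the person-time range of 3.0% to 14.3% rests on an assumed 20 to 100 switchers.

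The severity is minor: the tables are descriptive, the listings are complete, and efficacy, sample size and power are untouched. It is still worth correcting, because AE rates are a stated measure of tolerability. The retention wording is a secondary point of consistency between sections.

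**What to change.** **SAP 9.1.** In both dated bullets, replace the Week 36 end with: up to the patient's final visit (Week 36, or Week 48 for patients who switch to BOTOX). If the first lock needs a Week 36 cut, describe it there as a data cut only, not as part of the TEAE definition. SAP 9 and 9.1.1 then need no change.

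**Protocol 3.1 and SAP 3.1.** Add the exception that patients who stop BOTOX are exited under Protocol 8.8 and SAP 7.2, with the exit visit no earlier than about 12 weeks after the last injection, as Protocol 3.3 and 5.7 already require.

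**Cost.** The main fix is SAP wording only, with no new visits or data. The secondary point is one clarifying sentence in each document; the protocol sentence can wait for the next amendment.

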8.9 Withdrawal Criteria

Female patients must be withdrawn from the study if they become pregnant (see Section 4.5.1.1). Patients who have replied with “yes” to questions 4 or 5 in the suicidal ideation section or “yes” to any question in the suicidal behavior section of the C-SSRS should not receive any further study treatments, must be withdrawn from the study and should receive appropriate follow-up as in routine clinical practice.

8.10 Study Termination

The study may be stopped at his/her study site at any time by the site investigator. Allergan may stop the study (and/or the study site) for any reason with appropriate notification.

9. Adverse Events

Adverse events occurring during the study will be recorded on an adverse event case report form. If adverse events occur, the first concern will be the safety of the study participants.

9.1 Definitions

9.1.1 Adverse Event

An adverse event is any untoward medical occurrence in a patient or clinical investigation subject administered a pharmaceutical product and that does not necessarily have a causal relationship with this treatment. An adverse event can therefore be any unfavorable and unintended sign (including an abnormal laboratory finding), symptom, or disease temporally associated with the use of a medicinal (investigational) product, whether or not related to the medicinal (investigational) product. In addition, during the screening period, adverse events will be assessed regardless of the administration of a pharmaceutical product.

Note: Adverse events must be collected once informed consent has been obtained, regardless of whether or not the patient has been administered study drug.

Progression of treatment indication including new or worsening of anticipated clinical signs or symptoms, which are collected as clinical efficacy variables and assessed as unequivocally associated with the disease progression and /or lack of efficacy, should NOT be reported as adverse events unless the disease progression is greater than anticipated in the natural course of the disease.

Adverse events will be assessed, documented, and recorded in the eCRF throughout the study (ie, after informed consent has been obtained). All adverse events prior to study treatment from the time of informed consent are collected and defined as Pre-Treatment Adverse Event (PTAE). At each visit, the investigator should begin by querying for adverse events by asking each patient a general, non-directed question such as “How have you been feeling since the last visit?” Directed questioning and examination will then be done as appropriate. All reported adverse events will be documented on the appropriate eCRF.

If the patient reports an AE of cognitive impairment, in addition to completing the detailed questions on the AE eCRF, the clinician should indicate the patient’s response on the GCIA eCRF. This assessment aims to provide context for the complex symptoms associated with cognitive impairment.

